APPENDIX B: ACC/AHA HCM DIAGNOSTIC CRITERIA

GENETIC TESTING STRATEGIES/FAMILY SCREENING — RECOMMENDATIONS

CLASS I

1. Evaluation of familial inheritance and genetic counselling is recommended as part of the assessment of patients with HCM
2. Patients who undergo genetic testing should also undergo counseling by someone knowledgeable in the genetics of cardiovascular disease so that results and their clinical significance can be appropriately reviewed with the patient
3. Screening (clinical, with or without genetic testing) is recommended in first-degree relatives of patients with HCM
4. Genetic testing for HCM and other genetic causes of unexplained cardiac hypertrophy is recommended in patients with an atypical clinical presentation of HCM or when another genetic condition is suspected to be the cause

CLASS IIa

1. Genetic testing is reasonable in the index patient to facilitate the identification of first-degree family members at risk for developing HCM

CLASS IIb

1. The usefulness of genetic testing in the assessment of risk of Sudden Cardiac Death (SCD) in HCM is uncertain

CLASS III: NO BENEFIT

1. Genetic testing is not indicated in relatives when the index patient does not have a definitive pathogenic mutation
2. Ongoing clinical screening is not indicated in genotype negative relatives in families with HCM

GENOTYPE-POSITIVE/PHENOTYPE-NEGATIVE PATIENTS — RECOMMENDATION

CLASS I

1. In individuals with pathogenic mutations who do not express the HCM phenotype, it is recommended to perform serial ECG, Transthoracic Echocardiogram (TTE), and clinical assessment at periodic intervals (12 to 18 months in children and adolescents and about every 5 years in adults), based on the patient's age and change in clinical status

ELECTROCARDIOGRAPHY — RECOMMENDATIONS

CLASS I

1. A 12-lead ECG is recommended in the initial evaluation of patients with HCM
2. Twenty-four-hour ambulatory (Holter) electrocardiographic monitoring is recommended in the initial evaluation of patients with HCM to detect ventricular tachycardia (VT) and identify patients who may be candidates for ICD therapy
3. Twenty-four-hour ambulatory (Holter) electrocardiographic monitoring or event recording is recommended in patients with HCM who develop palpitations or light-headedness
4. A repeat ECG is recommended for patients with HCM when there is worsening of symptoms.

5. A 12-lead ECG is recommended every 12 to 18 months as a component of the screening algorithm for adolescent first degree relatives of patients with HCM who have no evidence of hypertrophy on echocardiography
6. A 12-lead ECG is recommended as a component of the screening algorithm for first-degree relatives of patients with HCM

CLASS IIa

1. Twenty-four-hour ambulatory (Holter) electrocardiographic monitoring, repeated every 1 to 2 years, is reasonable in patients with HCM who have no previous evidence of VT to identify patients who may be candidates for ICD therapy
2. Annual 12-lead ECGs are reasonable in patients with known HCM who are clinically stable to evaluate for asymptomatic changes in conduction or rhythm (*i.e.*, AF).

CLASS IIb

1. Twenty-four-hour ambulatory (Holter) electrocardiographic monitoring might be considered in adults with HCM to assess for asymptomatic paroxysmal atrial fibrillation/atrial flutter.

IMAGING**Echocardiography — Recommendations****CLASS I**

1. A TTE is recommended in the initial evaluation of all patients with suspected HCM
2. A TTE is recommended as a component of the screening algorithm for family members of patients with HCM unless the family member is genotype negative in a family with known definitive mutations
3. Periodic (12 to 18 months) TTE screening is recommended for children of patients with HCM, starting by age 12 years or earlier if a growth spurt or signs of puberty are evident and/or when there are plans for engaging in intense competitive sports or there is a family history of SCD
4. Repeat TTE is recommended for the evaluation of patients with HCM with a change in clinical status or new cardiovascular event
5. A trans-esophageal echocardiogram (TEE) is recommended for the intraoperative guidance of surgical myectomy
6. TTE or TEE with intracoronary contrast injection of the candidate's septal perforator(s) is recommended for the intra-procedural guidance of alcohol septal ablation
7. TTE should be used to evaluate the effects of surgical myectomy or alcohol septal ablation for obstructive HCM

CLASS IIa

1. TTE studies performed every 1 to 2 years can be useful in the serial evaluation of symptomatically stable patients with HCM to assess the degree of myocardial hypertrophy, dynamic obstruction, and myocardial function
2. Exercise TTE can be useful in the detection and quantification of dynamic LVOT obstruction in the absence of resting outflow tract obstruction in patients with HCM
3. TEE can be useful if TTE is inconclusive for clinical decision making about medical therapy and in situations such as planning for myectomy, exclusion of subaortic membrane or mitral regurgitation secondary to structural abnormalities of the mitral valve apparatus, or in assessment for the feasibility of alcohol septal ablation
4. TTE combined with the injection of an intravenous contrast agent is reasonable if the diagnosis of apical HCM or apical infarction or severity of hypertrophy is in doubt,

particularly when other imaging modalities such as Cardiovascular Magnetic Resonance (CMR) are not readily available, not diagnostic, or are contraindicated

5. Serial TTE studies are reasonable for clinically unaffected patients who have a first-degree relative with HCM when genetic status is unknown. Such follow-up may be considered every 12 to 18 months for children or adolescents from high-risk families and every 5 years for adult family members

CLASS III: NO BENEFIT

1. TTE studies should not be performed more frequently than every 12 months in patients with HCM when it is unlikely that any changes have occurred that would have an impact on clinical decision making
2. Routine TEE and/or contrast echocardiography is not recommended when TTE images are diagnostic of HCM and/or there is no suspicion of fixed obstruction or intrinsic mitral valve pathology

STRESS TESTING — RECOMMENDATIONS

CLASS IIa

1. Treadmill exercise testing is reasonable to determine functional capacity and response to therapy in patients with HCM
2. Treadmill testing with monitoring of an ECG and blood pressure is reasonable for SCD risk stratification in patients with HCM
3. In patients with HCM who do not have a resting peak instantaneous gradient of greater than or equal to 50 mm Hg, exercise echocardiography is reasonable for the detection and quantification of exercise-induced dynamic LVOT obstruction

CARDIAC MAGNETIC RESONANCE — RECOMMENDATIONS

CLASS I

1. CMR Imaging is indicated in patients with suspected HCM when echocardiography is inconclusive for diagnosis
2. CMR Imaging is indicated in patients with known HCM when additional information that may have an impact on management or decision making regarding invasive management, such as magnitude and distribution of hypertrophy or anatomy of the mitral valve apparatus or papillary muscles, is not adequately defined with echocardiography

CLASS IIa

1. CMR Imaging is reasonable in patients with HCM to define apical hypertrophy and/or aneurysm if echocardiography is inconclusive

CLASS IIb

1. In selected patients with known HCM, when SCD risk stratification is inconclusive after documentation of the conventional risk factors, CMR imaging with assessment of late gadolinium enhancement (LGE) may be considered in resolving clinical decision making
2. CMR Imaging may be considered in patients with LV hypertrophy and the suspicion of alternative diagnoses to HCM, including cardiac amyloidosis, Fabry disease, and genetic phenocopies such as *LAMP2* cardiomyopathy

DETECTION OF CONCOMITANT CORONARY DISEASE — RECOMMENDATIONS***CLASS I***

1. Coronary arteriography (invasive or computed tomographic imaging) is indicated in patients with HCM with chest discomfort who have an intermediate to high likelihood of Coronary Artery Disease (CAD) when the identification of concomitant CAD will change management strategies

CLASS IIa

1. Assessment of coronary anatomy with computed tomographic angiography is reasonable for patients with HCM with chest discomfort and a low likelihood of CAD to assess for possible concomitant CAD
2. Assessment of ischemia or perfusion abnormalities suggestive of CAD with single photon emission computed tomography (SPECT) or positron emission tomography (PET) myocardial perfusion imaging (MPI; because of excellent negative predictive value) is reasonable in patients with HCM with chest discomfort and a low likelihood of CAD to rule out possible concomitant CAD

CLASS III: NO BENEFIT

1. Routine SPECT MPI or stress echocardiography is not indicated for detection of “silent” CAD-related ischemia in patients with HCM who are asymptomatic
2. Assessment for the presence of blunted flow reserve (microvascular ischemia) using quantitative myocardial blood flow measurements by PET is not indicated for the assessment of prognosis in patients with HCM

APPENDIX C: DISCONTINUATION FOR PERSISTENT CLINICAL LABORATORY ELEVATIONS

A patient will be discontinued from the study if persistent elevations in ALT or AST, occur according to the following criteria:

- If a patient develops an elevation in ALT or AST $>5 \times$ ULN, the test will be repeated within 7 days.
 - If, upon re-test, ALT or AST remains $>5 \times$ ULN, study drug should be stopped and the patient discontinued from the study.
 - If, upon re-test, ALT or AST is $\leq 5 \times$ ULN, the patient may continue in the study and follow-up will be performed at regular study visits with unscheduled visits as needed at the discretion of the Investigator.
- The patient will be followed as clinically indicated/necessary until the abnormality reverts to normal or to patient's baseline level or until the abnormalities stabilize.

If at any time during the study a patient develops elevations in ALT or AST $>5 \times$ ULN, the study site will be alerted by the central laboratory.

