4.4.3 Dose-Adjustment of Study Drug

Throughout the dosing period the following will apply:

- 1) PEX dose may be decreased at any time for suspected elevated PEX levels or related AE.
- 2) Possible PEX dose levels will be:
 - a. Period 1: 35, 70, 105, 140, 175, and 210 mg (tablet strength of 35 mg).
 - b. Period 2: 35, 70, 105, 140, 175, 210, 245, and 280 mg (tablet strength of 35 mg).
- 3) In general, only one dose adjustment should be made per two-week period starting at the end of week 2 in Period 1. If the PI thinks an additional dose adjustment should be made, the PI should contact the Medical Monitor.
- 4) Upon notification of a dose adjustment the site should contact patient as soon as possible to initiate dose adjustment.

- 5) To achieve the higher target range for PEX in Period 2, the dose will initially be adjusted based on the plasma PEX level measured at Week 6 in Period 1. This dose adjustment will be performed at the end of the Week 8 visit (start of Period 2) in accordance with the Period 2 column in Table 4.1. **Important:** Any change made at Week 6 will need to be accounted for when adjusting the dose at Week 8.
- 6) Dose adjustments will proceed based on the following criteria (see Table 4.1):

Table 4.1 Possible dose-adjustments in Periods 1 and 2

Systemic Perhexiline Levels (PEX) (ng/mL)**	Period 1 (Weeks 2 – 8)	Period 2 (Weeks 9 – 16)
	Target Range 100-300 ng/mL Start Dose of 70 mg/day, 2 tablets/day (tablets to be taken orally in the evening) Maximum Dose 210 mg (6 tablets)	Target Range 300-500 ng/mL Start dose will be the dose-adjustment decision based on the Period 1, Week 6 level of PEX† (tablets to be taken orally in the evening) Maximum Dose 280 mg (8 tablets)
< 50	+2 tablets per day#	+2 tablets per day#
50 to 100	+1 tablet per day#	+2 tablets per day#
101 to 200	No change	+1 tablet per day#
201 – 300	No change	+1 tablet per day#
301 – 400	-1 tablet per day*	No change
401 – 500	-2 tablets per day*	No change
501 – 600	-3 tablets per day*	-1 tablet per day*
601 – 700	Discontinue for 1 day, and -3 tablets per day*	Discontinue for 1 day, and -2 tablets per day*
701 - 900	Discontinue for 3 days, and -4 tablets per day*	Discontinue for 1 day, and -3 tablets per day*
901 - 1200	Discontinue for 7 days, and -5 tablets per day*	Discontinue for 3 days, and -4 tablets per day*
> 1200	Discontinue for 7 days, and -5 tablets per day*	Discontinue for 7 days, and -5 tablets per day*

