4.6 PATIENT WITHDRAWAL AND DISCONTINUATION

Patients have the right to withdraw from the study at any time without needing to give any reason. Should a patient withdraw, all efforts should be made to complete and report observations prior to withdrawal as thoroughly as possible. Patients who choose to discontinue from the study will not be replaced.

The Investigator may withdraw patients in the event of intercurrent illness, AEs, protocol violations, administrative or other reasons. The Investigator is strongly encouraged to contact the Medical Monitor prior to discontinuation of study drug or withdrawal of patient from the study.

Discontinuation of PEX or discontinuation from the study is **mandatory** for:

- Patients whose baseline VO₂MAX is more than ±20% of their screening VO₂MAX, *i.e.*;
(*BASELINE VO₂MAX* – *SCREEN VO₂MAX*)/ *SCREEN VO₂MAX* > ±20%
- Patients who are unable or unwilling to return to the study site to repeat a CPEX test that did not meet the prospectively defined acceptance criteria as determined by the centralized CPEX assessor
- Patients identified as PMs of PEX at the week 1 (day 8) study visit. Despite the screening genotyping, which is 95-97% effective at identifying PMs, there may be a limited number of phenotypic PMs. Phenotypic PM subjects will be identified by determination of the PEX metabolic ratio (MR). This MR is the ratio of CIS to the parent compound, PEX. If the CIS:PEX is <0.4, the patient will be deemed a phenotypic PM regardless of genotype. These patients are at risk for clinically significant elevated plasma PEX levels. Such elevated plasma levels could decrease tolerability or increase the risk of short, self-limited toxicity; if unchecked longer term toxicities could result. Hence, as with the genotypic PMs, these phenotypic PM subjects will be withdrawn from the study. (Patients with a CIS:PEX ratio <0.4 after the week 1 visit will not automatically be withdrawn from the study. These patients should be further evaluated and the patient status will be discussed with the Medical Monitor.)
- Patients with persistent elevations in ALT or AST; see Appendix C for the definition of “persistent”
- Female study participants discovered to be pregnant during the treatment period

Discontinuation of PEX should be considered in the following situations [Phan *et al.*, 2009a] following discussion with the Medical Monitor:

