6 STUDY SCHEDULE AND ACTIVITIES

6.1 SCHEDULING WINDOWS FOR STUDY PROCEDURES AND EVALUATIONS

The scheduling windows for the various timepoints for study procedures and evaluations are summarized in Table 6.1, below. Study procedures and evaluations should be scheduled to commence in the morning of each study site visit.

Table 6.1 Time windows for study procedures and evaluations

Timepoint	Permitted Time Window
Screening	In the 28 days before the Baseline visit
Baseline Visit (Day 1)	This is time zero for the study and all other visit dates will be estimated in reference to this visit
Day 8 (± 1 Day), End Week 1 / Start Week 2, Period 1	Day 7, 8, or 9; following at least the first 6 days of study-drug dosing
Day 15 (± 1 Day), End Week 2 / Start Week 3, Period 1	Day 14, 15 or 16; following at least the first 13 days of study-drug dosing
All other timepoints	± 3 Days. Subject should be taking study-drug until the day prior to the End of Treatment visit.

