6.2 SCHEDULE OF ASSESSMENTS

The flowchart of procedures, measurements and other assessments is shown in table 6.2.

Table 6.2 Schedule of Time and Events for Protocol Activities

Complete Schedule of Protocol Activities	Screening [A]	Baseline Week 1 (Day 1) [A]	After Completion of Week 1 (Day 8)	After Completion of Weeks 2, 4, 6, 8, 10, 12 & 14 (Days 15, 29, 43, 57, 71, 85 & 99)	End of Treatment After Completion of Week 16 (Day 113)	Final Visit Week 20 (Day 140)
Time window permitted	-28 days	n.a.	±1 Day	±1 Day for Week 2 ±3 Days for other timepoints	±3 Days	±3 Days
Informed Consent	X					
Inclusion/Exclusion Criteria	X	X [B]				
Demographics, Medical History, Physical Exam	X					
12-lead ECG [C, D]	X	X [E]		X	X	X
CPEX Testing [D, F]	X	X [G]		After End of Week 8	X [H]	
Weight	X	X		After End of Week 8	X	X
Vital Signs [I]	X	X		X	X	X
Laboratory Procedures [J]						
Serum Pregnancy Test [K]	X					X
Urine Pregnancy Test [J, K]		X				
Serum Chemistry [L]	X			After End of Week 8	X	X
Complete Blood Count [M]	X				X	X
Coagulation Tests [N]	X					
CYP2D6 Screening [O]	X					
Plasma PEX, CIS & TRANS [P]			X	X	X	X
Biomarkers (Hemoglobin A1c)	X			After End of Week 8	X	X
Study Dosing & Dose Adjustment as per Guidelines & Algorithm [Q]		Start at 70 mg [R]	X	X		
Review of Dosing Instructions and Adherence to Dosing		X	X	X	X	
Adverse Event Assessment [S]	X	X	X	X	X	X
Adverse Device Effect Assessment [T]			X	X	X	X
Concomitant Medication Review [U]	X	X	X	X	X	X
6 Minute Walk Test (6MWT) [D]		X		After End of Week 8	X	

Footnotes:

- A.** The Screening visit must be performed within 28 days prior to dosing.
- B.** Entry criteria to be evaluated: Baseline CPEX compared to Screening CPEX, and ECG exclusion criteria
- C.** ECGs should be done in triplicate prior to blood draws when possible and obtained after the patient has been resting comfortably in a supine position for approximately 10 minutes.
- D.** ECGs will be done first, the CPEX test will be second, and the 6MWT will be the last procedure completed during any visit by the patient to the study site in order to facilitate the patient's ability to adequately complete a CPEX and a 6MWT in a single day
- E.** The baseline ECG must not meet any of the exclusion criteria detailed in section 4.3.2; this must be confirmed by the central ECG reader before study-drug can be dispensed to the patient
- F.**

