3.2.2 Safety Laboratory Evaluations

Serum Chemistry

Blood samples were to be obtained for routine serum chemistry safety tests at Screening, and repeated at the end of Period 1 (Week 8), at the end of Period 2 (Week 16) and at Follow-up (planned for Week 20) visit. The following safety chemistry parameters levels were to be assessed by a central laboratory:

- Sodium [mmol/L]
- Potassium [mmol/L]
- Bicarbonate [mmol/L]
- Chloride [mmol/L]
- Calcium [mmol/L]
- Phosphorus [mmol/L]
- Glucose [mmol/L]
- Creatinine [μ mol/L]
- BUN [mmol/L]
- Creatine Kinase [U/L]
- Uric acid [μ mol/L]
- Albumin [g/L]
- Total protein [g/L]
- AST (SGOT) [U/L]
- ALT (SGPT) [U/L]
- Alkaline phosphatase [U/L]
- Total bilirubin [μ mol/L]
- Lactate dehydrogenase (LDH) [U/L]
- Total cholesterol [mmol/L]

The Baseline value for each parameter will be identified as the last assessment value taken prior to the start of study medication. For most parameters and most patients, this will be taken as the Screening assessment, however, if any patients have an unscheduled assessment after their Screening assessment and before starting study medication, this will be used.

The change and percentage change from Baseline to the end of Period 1 (Week 8), end of Period 2 (Week 16) and Follow-up (Week 20) assessment will also be derived.

For transaminases, any assessments that are outside the following upper limit of normal (ULN) threshold multiples will be identified electronically in the analysis dataset:

AST (SGOT) [U/L]	> 3 x ULN
ALT (SGPT) [U/L]	> 3 x ULN
Alkaline phosphatase [U/L]	> 2.5 x ULN
Total bilirubin [mg/dL]	> 2 x ULN

Complete Blood Count

Blood samples were to be obtained for complete blood count at Screening, and repeated at the end of the study, Period 2 (Week 16), and Follow-up (Week 20) assessment. The following parameters levels were to be assessed by a central laboratory:

- Hemoglobin [g/L]
- Hematocrit [%]
- Red blood cells (RBC) [$10^{12}/L$]
- MCV [fL]
- MCH [pg]
- MCHC [g/L]
- White blood cells [$10^9/L$]
- Neutrophils [$10^9/L$ and %]
- Lymphocytes [$10^9/L$ and %]
- Monocytes [$10^9/L$ and %]
- Eosinophils [$10^9/L$ and %]
- Basophils [$10^9/L$ and %]
- Platelets [$10^9/L$]

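### No scheduled ALT/AST sample can trigger the mandatory drug stop for an elevation that first arises in Period 2

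*Protocol*

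**What the plan says.** **The rule.** Protocol 4.6 includes this in its mandatory discontinuation list: "Patients with persistent elevations in ALT or AST; see Appendix C for the definition of" persistent. Appendix C gives the definition. A value above 5 x ULN is repeated within 7 days, and if it is still above 5 x ULN, "study drug should be stopped and the patient discontinued from the study". If the repeat is at or below 5 x ULN the patient may continue, and "follow-up will be performed at regular study visits with unscheduled visits as needed at the discretion of the Investigator". For any value above the limit, "the study site will be alerted by the central laboratory".

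**The sampling.** Protocol Table 6.2 has one column for the two-weekly visits, "After Completion of Weeks 2, 4, 6, 8, 10, 12 & 14 (Days 15, 29, 43, 57, 71, 85 & 99"; within it, serum chemistry is marked for Week 8 only. Section 6.6 lists vital signs, ECG, drug levels, adverse events and medications for these visits, and 6.7 adds chemistry at Week 8 alone. SAP 3.2.2 agrees: after Screening, chemistry is "repeated at the end of Period 1 (Week 8), at the end of Period 2 (Week 16) and at Follow-up".

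**The dosing.** Protocol 4.4.3 says of the first Period 2 adjustment: "This dose adjustment will be performed at the end of the Week 8 visit (start of Period 2". At the other end, Table 6.1 states: "Subject should be taking study-drug until the day prior to the End of Treatment visit". Section 6.8 repeats this and has the remaining tablets collected at that visit.

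**The concern.** A rule that acts on an enzyme value needs an enzyme sample taken while there is still dosing to stop. In Period 2 the two scheduled samples sit on either side of the dosing. The first is drawn before the move to the higher target, the second after the last tablet.

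Period 2 is the higher-exposure period (300-500 ng/mL, up to 280 mg daily), and Protocol 2.3 names liver toxicity among the drug's most notable side effects. A patient whose transaminases rise without symptoms after Day 57 would, on schedule, be treated up to the last dose on Day 112. The stake is individual patient safety. The VO2MAX analyses are not affected.

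The protocol's other measurement-based hold rule is matched to its sampling: the QTcF/JTcF rule in 4.4.4 is served by an ECG at every two-weekly visit. The ALT/AST rule has no such match.

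**Working it through.** The plan states no figure to reproduce here; the check is day arithmetic on the schedule.

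**Inputs**
- Chemistry on Days 57 and 113; blood draws for drug levels on Days 71, 85 and 99; windows of +/-3 days (Protocol Table 6.2).
- Last dose the day before the Week 16 visit, nominally Day 112 (Protocol 6.1, 6.8).
- Visits in the morning, doses in the evening (Protocol 6.1, 4.4.1).
- Retest within 7 days (Appendix C).

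**Step 1: the gap.** 113 - 57 = 56 days. With windows, the shortest is 110 - 60 = 50 and the longest 116 - 54 = 62.

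**Step 2: dosing left when the Week 16 sample is drawn.** For a visit on Day 110, 113 or 116 the last dose was on Day 109, 112 or 115, so 0 dosing days remain in each case. The retest could fall as late as Day 117, 120 or 123.

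**Step 3: the Week 8 sample.** It can still stop drug early in Period 2, but only for an elevation already present on Day 57. For one that first arises in Period 2, the number of scheduled samples able to trigger the stop is 0.

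**Step 4: effect of sampling at Weeks 10, 12 and 14.** The intervals become 71 - 57, 85 - 71, 99 - 85 and 113 - 99, each 14 days. Onsets up to Day 99 are covered by an on-drug sample: 99 - 57 = 42 of 56 days.

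**Step 5: dosing days avoided.** Let t be the days from first sample to confirmed stop. A stop on day S avoids that evening's dose, so days avoided = 112 - S + 1 = 113 - (sample day) - t, with a floor of 0. Chemistry turnaround is not stated. Three cases are assumed: t = 7 (immediate results, retest on the seventh day), t = 3 + 7 + 3 = 13 and t = 5 + 7 + 5 = 17. The last two borrow the 3-5 days that Protocol 4.4.2 gives for the drug-level assay.

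| Sample | t = 7 | t = 13 | t = 17 |
|---|---|---|---|
| Week 10 (113 - 71 = 42) | 35 | 29 | 25 |
| Week 12 (113 - 85 = 28) | 21 | 15 | 11 |
| Week 14 (113 - 99 = 14) | 7 | 1 | 0 |

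At the least favorable windows (sample 3 days late, last dose Day 109) each entry falls by 6, with a floor of 0: 29/23/19, 15/9/5 and 1/0/0. All three cases use the full 7 days for the retest, so a faster retest saves more.

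**Step 6: expected cases.** The documents give no rate of ALT/AST above 5 x ULN. For an assumed 8-week rate p, 30 patients and uniform onset, all Period 2 cases = 30p and reachable cases = 30p x 42/56.

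| p | All cases | Reachable |
|---|---|---|
| 0.5% | 0.15 | 0.11 |
| 1% | 0.30 | 0.23 |
| 2% | 0.60 | 0.45 |
| 5% | 1.50 | 1.13 |

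Reachable here means sampled on drug. At t = 17 the Week 14 sample nominally saves no dosing, so onsets for which dosing is avoided shrink to 85 - 57 = 28 of 56 days, and the last column to 0.075, 0.15, 0.30 and 0.75.

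**The case against.** The strongest reply is that sampling frequency is a judgment and nothing in the documents sets a shorter interval. The plan's chosen liver control is exposure. Drug levels are measured every two weeks, with dose cuts above 500 ng/mL and dose holds above 600 ng/mL in Period 2. Poor metabolizers, known chronic liver disease and ALT/AST above 1.5 x ULN are excluded at entry. The 300-500 ng/mL target lies inside the 150-600 ng/mL window of Protocol 2.8.1. Adverse events are reviewed every two weeks, investigators may withdraw patients, and the Study Monitoring Team reviews laboratory listings about every two months once 25% are enrolled.

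All of that stands as reason to expect few cases. None of it measures ALT or AST in the individual patient between Days 57 and 113. The monitoring team sees only samples that were drawn. The central laboratory can alert only on a sample it receives. The unscheduled visits in Appendix C are for a patient already flagged whose retest came back at or below 5 x ULN. The blood sample at early withdrawal (6.11) follows the decision to leave.

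A reader might go further and infer that the stopping rule cannot work in Period 2, or that Period 2 dosing is unsafe. The documents do not support either. An elevation present on Day 57 can still stop drug, as can any unscheduled sample, and no event rate is given from which to argue harm. A reader might also infer that a Week 14 sample comes too late to help. With evening dosing and a 7-day path it avoids 7 doses, and it is the only one of the three added draws that covers onsets between Days 85 and 99.

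**Conclusion.** The point holds as a gap in the safety schedule: for a symptomless ALT/AST elevation that first arises in Period 2, no scheduled sample can trigger the stop that 4.6 and Appendix C make mandatory. It is not a contradiction between the documents; the protocol and SAP agree on the schedule. The Day 113 sample still has a use, since it can start the retest and follow-up.

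The 56-day gap and the absence of dosing after the Week 16 sample rest on the documents alone. The dosing days avoided depend on the assumed times to a confirmed stop. The case counts depend on assumed rates and uniform onset, and restricting them to symptomless, confirmed elevations would lower them further. At about 0.11 to 1.1 reachable cases among 30 patients, this is a modest safety improvement, worth making because it is cheap.

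**What to change.** Amend Protocol Table 6.2 and section 6.6 to add ALT and AST to the blood draws already made at Weeks 10, 12 and 14, and ask for a prompt retest of any value above 5 x ULN rather than one at the end of the 7 days.

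SAP 8.3 counts patients over the transaminase thresholds by period, and each period now has one scheduled sample. With the added draws Period 2 would have four (Weeks 10, 12, 14 and 16) against one in Period 1, which would inflate its count. Add a sentence keeping that comparison on the Week 8 and Week 16 samples, with the added results reported separately.

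The cost is an amendment approved by the IRB/IEC (Protocol 10.2), 3 x 30 = 90 to 3 x 33 = 99 extra ALT/AST assays, an occasional extra visit for a retest because routine visits are 14 days apart, and the one sentence in the SAP. No new routine visit or venepuncture is needed. If dosing is already complete, the change belongs in the phase 3 study that Protocol 2.8 says this trial is meant to inform.
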